The Eligibility Screening will consist of the following questions:

- 1) Are you between ages 18-99 years old? [YES TO QUALIFY]
- 2) Have you ever used the SinuSonic device? [NO TO QUALIFY]
- 3) Do you meet any of the conditions listed under the Safety and Warnings for use of the SinuSonic device? [NO TO QUALIFY]
 - a) Current or history of breathing problems (i.e., asthma, chronic obstructive pulmonary disorder (COPD), chronic bronchitis, emphysema, pneumonia, pleural effusion, lung cancer, cancer of the throat or upper airway)

- b) Current or history of circulatory problems (i.e., active nose bleed, heart arrhythmia, coronary artery disease, congestive heart failure, heart attack)
- c) Other conditions, specified as brain tumor, moderate to severe ear pain, fever greater than 101 degrees

- 4) Have you experienced symptoms of nasal congestion that have persisted at least 2 weeks? [YES TO QUALIFY]
- 5) Is your current level of nasal congestion at 5 or higher? (VAS included here) [YES TO QUALIFY]

Step 2: Consent/Linkage File

When all eligibility criteria are met, individuals will be invited to access the Informed Consent document (also provided via RedCap) to read and e-sign. Phone number and email address for the researcher will be provided in the event of questions or request for clarification.

After receiving the e-signed informed consent, researchers will assign a SubjectID number so that the participant can use the SubjectID number when completing all questionnaire assessment sessions using RedCap. Researchers will maintain a database linking SubjectID and name on their password-protected computers that will not be accessible to anyone who is not affiliated with the research.

Step 3: Pre-SinuSonic assessment

Participants will be asked to complete this assessment, via RedCap, prior to beginning use of the SinuSonic. Researchers will provide participants with a link to the assessment (text or email), along with their unique SubjectID number to use. The following instruments will be programmed into RedCap for completion:

Prior to SinuSonic Use (week 0):

- 1) Demographic Information Form
- 2) SF12 to assess overall health ("how you feel and how well you are able to do your usual activities")
- 3) TNSS to assess current nasal symptoms
- 4) BPQ to reflect perception of autonomic regulation
- 5) HADS to assess anxiety and depression
- 6) ATES to assess history of trauma/adverse events

Step 4: SinuSonic Use / Weekly assessments

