After completing the pre-SinuSonic assessment, researchers will inform participants to begin directed use of the SinuSonic (2 minutes per day, 2 times per day). Participants will be asked to confirm SinuSonic use on a weekly questionnaire. Additionally, participants will be asked to complete the following questionnaires approximately 5 minutes after final SinuSonic use for that week. The following instruments will be programmed into RedCap for completion:

Weekly, for 4 weeks (end of week 1, 2, 3, 4).

- 1) TNSS to assess current nasal symptoms
- 2) PGIC to reflect change in activity limitations, symptoms, emotions and overall quality of life

Step 5: Final research assessment

Participants will be asked to confirm use of the SinuSonic on a weekly questionnaire. Additionally, participants will be asked to complete the following questionnaires approximately 5 minutes after final SinuSonic use on the 5th consecutive week. The following instruments will be programmed into RedCap for completion:

End of Study (end of week 5).

- 1) TNSS to assess current nasal symptoms
- 2) PGIC to reflect change in activity limitations, symptoms, emotions and overall quality of life
- 3) BPQ to reflect perception of autonomic regulation
- 4) HADS to assess anxiety and depression

Description of Measures

Body Perception Questionnaire (BPQ) (Cabrera et al., 2018). The Body Perception Questionnaire (BPQ) is a self-report measure of body awareness and autonomic reactivity. Its items are based on the organization of the autonomic nervous system (ANS), a set of neural pathways connecting the brain and body. These pathways send information from the body about the status of organs and tissues (i.e., afferent projections). Some of these incoming signals form a basis for the subjective awareness of the body. The ANS also carries signals that control the functions of these organs and tissues (i.e., efferent projections). These signals can alter the functions of the body, depending on internal and external needs. Only the Autonomic Reactivity subscale will be distributed and used for the current study.

Hospital Anxiety and Depression Scale (HADS) (Zigmond & Snaith, 1983). HADS is a fourteen-item scale with seven items each for anxiety and depression subscales. Scoring for each item ranges from zero to three. A subscale score >8 denotes anxiety or depression.

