Short-Form Health Survey-12 (Ware et al., 1995). The SF-12 is a health-related quality-of-life questionnaire consisting of twelve questions that measure eight health domains to assess physical and mental health. Physical health-related domains include General Health (GH), Physical Functioning (PF), Role Physical (RP), and Body Pain (BP)

Total Nasal Symptom Score. The Total Nasal Symptom Score (TNSS) is the sum of scores for each of nasal congestion, sneezing, nasal itching, and rhinorrhea at each time point, using a four point scale (0–3), where 0 indicates no symptoms, a score of 1 for mild symptoms that are easily tolerable, 2 for awareness of symptoms which are bothersome but tolerable and 3 is reserved for severe symptoms that are hard to tolerate and interfere with daily activity. TNSS is calculated by adding the score for each of the symptoms to a total out of 12.

Adverse Traumatic Experiences Scale (ATES) (Kolacz et al., 2020). This measure asks about childhood adverse experiences, childhood maltreatment, other person maltreatment, life-threatening situations, sudden deaths of close ones, and personal health situations. Respondent-reported prior adverse events

of maltreatment, life-threatening situations, and sudden deaths of close ones are summed to create an adversity score (range: 0–19).

Patient Global Impression of Change (PGIC) (Hurst & Bolten (2004). The self-report measure Patient Global Impression of Change (PGIC) reflects a patient's belief about the efficacy of treatment. PGIC is a 7 point scale depicting a patient's rating of overall improvement. Patients rate their change as "very much improved," "much improved," "minimally improved," "no change," "minimally worse," "much worse," or "very much worse."

Data Analyses

Questionnaire data will be entered by participants into RedCap for researcher access. Researchers will export the data into SPSS for data analyses. All databases will be stored on password protected computers, accessible only to researchers affiliated with the study, and backed up on UNC servers.

As the current proposal is for a feasibility/pilot study, researchers will evaluate the following aims to determine whether a larger, randomized trial is warranted.

Aim 1: Examine associations between nasal congestion, autonomic functioning, adverse events, and mental health indices (depression, anxiety) at baseline. Pearson correlation analyses will be used to evaluate relationships among measures at each timepoint.

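### The week-5 survey lists a rating of change directly before BPQ and HADS, with no counterpart at week 0, so their before-after change could carry a question-order effect of unknown size and direction

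*Combined protocol and SAP*

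**What the plan says.** Step 3 numbers six instruments for week 0: demographics, SF-12, TNSS, BPQ, HADS and ATES. BPQ is fourth and HADS fifth ("5) HADS to assess anxiety and depression"). None of the six asks the participant to rate change.

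Step 5 numbers four instruments for the end of week 5. TNSS is first and PGIC second, the latter described as "PGIC to reflect change in activity limitations, symptoms, emotions and overall quality of life". Then come "3) BPQ to reflect perception of autonomic regulation" and "4) HADS to assess anxiety and depression". Step 4 gives TNSS followed by PGIC at the end of each of weeks 1 to 4.

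Description of Measures says that PGIC "reflects a patient's belief about the efficacy of treatment". Its seven response options run from three grades of improvement through no change to three grades of worsening.

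Under Data Analyses, hypotheses B and C compare BPQ and HADS between baseline and end of study by repeated measures ANOVA. Aim 4 takes effect sizes from the outcome measures to set the sample size of a later trial. Both steps say that the instruments will be programmed into RedCap. Neither says whether the on-screen order is the listed order, or whether it is fixed or randomised.

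**The concern.** A before-after difference is easiest to interpret when both scores are taken in the same question context. Here, if the lists are followed, the contexts differ in a way that bears on the outcome. At week 5 a participant records a view of how they have changed, with emotions in scope by the plan's own description, and then answers items on autonomic reactivity, anxiety and depression. A wish to answer consistently could pull those scores towards the rating just given. At week 0 nothing comparable comes first.

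The design has little protection against this. There is one group, so no comparator would share the effect and cancel it. BPQ and HADS are measured only twice, so each result is a single difference. All outcomes are self-reported by people who bought the device. If everyone sees the same order, no later analysis can separate an order effect from real change. At stake are hypotheses B and C and, through Aim 4, the size of the next trial.

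**Working it through.** **Order check.**

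| Position | Week 0 (Step 3) | Week 5 (Step 5) |
|---|---|---|
| 1 | Demographics | TNSS |
| 2 | SF-12 | PGIC |
| 3 | TNSS | BPQ |
| 4 | BPQ | HADS |
| 5 | HADS | none |
| 6 | ATES | none |

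TNSS, BPQ and HADS keep the same relative order at both times. At week 5 PGIC comes between TNSS and BPQ. SF-12 precedes BPQ and HADS at week 0 only.

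**Sensitivity.** The plan gives no alpha, power, SD, correlation or effect size for its 50 participants, so there is no stated figure to reproduce. The inputs are:

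- n = 50, from Participants, with every participant assumed to complete both surveys
- two-sided alpha of 0.05 (assumed)
- true change of zero (assumed)
- order-induced shift s of 0.05 to 0.20, in units of the score SD, taken as equal at both times (assumed)
- week-0/week-5 correlation r of 0.5, 0.7 or 0.8 (assumed)

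A repeated measures ANOVA with two time points is equivalent to a paired t-test. The standardised paired effect is dz = s / sqrt(2(1 − r)). The noncentrality is dz × sqrt(50). The rejection probability comes from the noncentral t distribution with 49 degrees of freedom and a critical value of 2.010.

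For example, with s = 0.10 and r = 0.7, dz = 0.10 / sqrt(0.6) = 0.129. The noncentrality is 0.129 × 7.071 = 0.913, and the rejection probability is 14.6%.

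| Shift (SD) | r = 0.5 | r = 0.7 | r = 0.8 |
|---|---|---|---|
| 0 | 5.0% | 5.0% | 5.0% |
| 0.05 | 6.4% | 7.3% | 8.5% |
| 0.10 | 10.7% | 14.6% | 19.5% |
| 0.15 | 18.0% | 26.9% | 37.6% |
| 0.20 | 28.4% | 43.3% | 59.2% |

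The test is two-sided, so a shift of either sign gives the same rate when there is no true change. If there were a real improvement, a shift towards worse would hide part of it.

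**Aim 4.** Take a later 1:1 trial with a true standardised effect of 0.40, two-sided 5% alpha and 80% power (all assumed). The number per arm is 2 × (1.960 + 0.842)² / 0.40² = 98.1, so 99. Planning on an inflated effect of 0.45, 0.50 or 0.60 gives 78, 63 or 44 per arm, and true power falls to about 70%, 61% or 47%. A bias the other way, to 0.30, would give 175 per arm, more than needed.

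**The case against.** A reader might infer that the plan builds in a bias towards improvement. The documents do not support that, for four reasons.

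- **Screen order is inferred.** The numbered lists suggest a presentation order but do not state it. This stands, and it is why the point is conditional on RedCap following the list.
- **Direction is unknown.** PGIC is a symmetric scale. A participant who answers no change or worse could be drawn the other way. Emotions are mentioned in the one-line gloss in Steps 4 and 5, while Description of Measures calls PGIC a rating of overall improvement. This stands too.
- **Size is wholly assumed.** The tables show what a shift of a given size would do. They do not show that this order produces one.
- **Reordering does not make the contexts equal.** By week 5 participants have already completed PGIC four times. They also confirm device use and answer about five minutes after using the device. SF-12 comes first only at week 0. All of this remains after the fix.

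There is also a cost to PGIC, which is itself an outcome under hypothesis A. As listed, it follows TNSS directly in every week from 1 to 5. Moved to the end at week 5, it would follow BPQ and the 14-item HADS at that visit only. This is a real but small drawback. It does not outweigh protecting the only two measurements on which the BPQ and HADS comparisons rest.

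Finally, the lack of a control group, expectancy among purchasers, and regression to the mean after selection for current congestion of 5 or higher affect the same differences whatever the order. The plan itself labels the Aim 2 tests as preliminary. That makes this point secondary, but it does not excuse an avoidable addition to those problems.

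**Conclusion.** The point holds in a limited form. The week-5 list puts a rating of change directly before BPQ and HADS, and the week-0 list has no counterpart. If RedCap follows the lists, the changes used for hypotheses B and C and for Aim 4 could carry an order effect that this single-group design cannot separate from real change.

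Its size and direction are unknown. The range of 6% to 59% rests on assumed shifts of 0.05 to 0.20 SD, assumed correlations of 0.5 to 0.8, 50 complete pairs and no true change. It measures how sensitive the tests are to a small shift and does not predict the bias. This is a minor, cheap improvement, not a fault that invalidates the pilot.

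**What to change.** Before launch, state the RedCap order in the protocol and set week 5 to TNSS, BPQ, HADS, then PGIC. Leave weeks 1 to 4 as listed, where PGIC already comes last. The shared measures then keep their week-0 relative order, and no change rating comes immediately before BPQ or HADS.

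The cost is one edit to the survey build, with no added items and no lost data. The drawback is that PGIC's context changes slightly at week 5 compared with weeks 1 to 4, which should be noted when PGIC is analysed across time. The remaining differences (PGIC in weeks 1 to 4, SF-12 only at week 0, no control group) should be named as limitations when the BPQ and HADS changes and the Aim 4 effect sizes are reported.

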As this is a feasibility/pilot study, data from the study will be used to estimate effect sizes and inform a larger, randomized trial on the effects of the SinuSonic on individuals with compromised autonomic regulation, if warranted by the results.

Background: The SinuSonic was developed as a non-pharmaceutical device aimed to reduce nasal congestion via simultaneous administration of acoustic vibration and gentle oscillating expiratory pressure. Previous studies have demonstrated significant improvements in congestion and ease of breathing after immediate use of the device (Cairns & Bogan, 2019) and after twice daily use for 5-weeks (Soler et al., 2020). In this study, there was significant improvement in peak nasal inspiratory flow after only 2 weeks of use, and significant improvement in multiple self-report measures of congestion after 5 weeks of use. No adverse effects were reported. A review report by Schlosser, Salley and Soler likewise concluded that the device may improve pregnancy-related rhinitis, which may be particularly important for individuals who would prefer non-pharmacological interventions while pregnant or breastfeeding (<https://sinusonic.com/blogs/learn/pregnancy-rhinitis.>)

[figure not shown]
There are common clinical symptoms, such as anxiety and depression, that are frequently associated in individuals who feel unhealthy. The Polyvagal Theory (Porges, 1995, 1998, 2001, 2003, 2007) provides a model for which these psychological and physical symptoms may be viewed as the predictable consequences of a common neural substrate. This neural substrate involves the neural regulation of the heart and lungs, as well as neural regulation of the muscles of the face and head which function together as a Ventral Vagal Complex (VVC).

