The VVC is based on the documented neuroanatomical and neurophysiological pathways between the brainstem areas that regulate the muscles of the face (via special visceral efferent pathways) and the heart and lungs (via the vagus). Features of the VVC may serve as a clinical checklist converging on symptoms of anxiety and depression as observed in several clinical disorders including autism (Bal et al., 2010; Patriquin et al., 2011; Porges et al., 2012; Van Hecke et al., 2009), Fragile-X-Syndrome (Heilman et al., 2011), selective mutism (Heilman et al., 2012), prematurity (Doussard-Roosevelt, et al., 1997), prenatal exposure to opiates and alcohol (Suess et al. 1997), PTSD (Sahar et al., 2001), perpetrators of domestic abuse (Umhau et al., 2002), Borderline Personality Disorder (Austin et al., 2007), behavioral regulation problems (Dale et al., 2011), and abuse and neglect (Dale et al., 2009). However, relating symptoms of anxiety and depression to an illness that impacts the functioning of the VVC (i.e., nasal congestion impacts the functioning of the vagus at the lungs) is a novel aspect of the current study.

Additionally, individuals who already have a compromised VVC due to adverse events (history or current), may also be at risk for the continued cycle of VVC complications (i.e., chronic congestion, anxiety and/or depression).

In summary, the function of the SinuSonic (i.e., reducing nasal congestion while improving vagal regulation of the lungs) align with the theoretical principles of the Polyvagal Theory. Thus, our proposed research will serve to determine whether the SinuSonic will have a significant impact on the reduction and management of physical and psychological symptoms (i.e., anxiety and depression), as they are described within the context of a dysregulated VVC.

Flowchart of Research Procedures:

Participants

50 adults (aged 18-99 years) with self-reported nasal congestion will be recruited for the study. Participants must be US residents.

Data Collection Procedures

Step 1: Recruit/Eligibility Screening

Individuals who make a purchase of the SinuSonic device will receive a recruitment flyer in the shipping box for their device, but only new users of the SinuSonic will be eligible to participate. The recruitment flyer will contain a QR code that users can scan to access the Eligibility Screening for the study in RedCap. Staff at SinuSonic has agreed to include the recruitment flyer when shipping packages.

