Aim 2: (*These would be the aims for a future, randomized clinical trial, with preliminary testing using data from the current feasibility/pilot study*): Evaluate the effect of the SinuSonic on users with chronic nasal congestion. We will focus on three constructs important to psychological and physical health and hypothesize that:

- A) Nasal congestion will significantly improve when comparing baseline measures to follow-up measures at each week, and will maintain effects at 5 weeks. Repeated measures ANOVA will be used to evaluate mean change in outcome measures across time in PGIC and TNSS.
- B) Autonomic functioning will significantly improve when comparing baseline measures to end of study. Repeated measures ANOVA will be used to evaluate mean change in BPQ across time.
- C) Mental health indices (depression, anxiety) will significantly improve when comparing baseline measures to end of study. Repeated measures ANOVA will be used to evaluate mean change in HADS across time.

Aim 3: (*This would be an aim for a future, randomized clinical trial, with preliminary testing using data from the current feasibility/pilot study*). Evaluate the mediating effect of current/previous adverse experiences on outcome measures at 5 weeks, using regression models.

Aim 4: Calculate effect sizes for each outcome variable, which will be necessary to determine adequate sample size for a future clinical trial. G-Power software will be used to determine sample sizes based on the effect sizes of the current outcome measures.

References

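### The feasibility/pilot study is to decide whether a randomized trial is warranted, but no aim analyses a feasibility outcome, no progression criterion is stated, and the device-effect evidence is uncontrolled

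*Combined protocol and SAP*

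**What the plan says.** The statement that follows the Purpose section reads "As this is a feasibility/pilot study, data from the study will be used to estimate effect sizes and inform a larger, randomized trial", with the larger trial to follow "if warranted by the results". The opening of Data Analyses repeats the feasibility/pilot label and ties the decision to the aims: "researchers will evaluate the following aims to determine whether a larger, randomized trial is warranted".

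The aims are:
- **Aim 1:** associations at baseline; "Pearson correlation analyses will be used to evaluate relationships among measures at each timepoint".
- **Aim 2:** hypotheses that congestion, autonomic functioning and mental health will each improve significantly from baseline. For part A, "Repeated measures ANOVA will be used to evaluate mean change in outcome measures across time in PGIC and TNSS"; parts B and C apply the same method to BPQ and HADS.
- **Aim 3:** regression models for mediation by adverse experiences.
- **Aim 4:** effect sizes for each outcome, entered into G-Power to size the future trial.

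Aims 2 and 3 carry a note that they are aims of a future randomized trial, tested here in a preliminary way.

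On the sample, Participants says "50 adults (aged 18-99 years) with self-reported nasal congestion will be recruited for the study". Step 1 recruits people who have bought the device, through a flyer in the shipping box. The eligibility screen asks "Is your current level of nasal congestion at 5 or higher". There is one group and no comparator. Screening, e-consent and all questionnaires run in RedCap, and the Purpose section says that the weekly questionnaires record the amount of device use.

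**The concern.** A study with this label, whose results decide on a randomized trial, would be expected to report whether people can be recruited, kept for five weeks and persuaded to complete the surveys and use the device. The plan collects the records that would show this but commits to analysing none of them. It also does not say what result would count for or against proceeding.

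What remains as evidence of device effect is uncontrolled. Participants are self-selected buyers who rate their own symptoms and are admitted at a time of higher congestion. Natural course, expectation and regression to the mean all push the change towards improvement.

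Two things are at stake. A decision to proceed could rest on drift. And the next trial could be sized on an effect that includes drift, with no dropout figure taken from this study.

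**Working it through.** **1. Aims against feasibility measures.** Each measure below can be obtained from records described in Steps 1 to 5 or the Purpose section.

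| Measure | Source in the plan | Analysed in an aim? |
|---|---|---|
| Consented per eligible screen, and per month | RedCap screener and e-consent | No |
| Week-5 retention | Step 5 questionnaires | No |
| Weekly survey completion | Step 4 and 5 questionnaires | No |
| Weekly device use | Weekly questionnaire | No |
| Progression criterion | None stated | Not applicable |

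**2. The plan's own figure.** The sample size of 50 comes with no alpha, power, SD, dropout or precision target, so there is nothing to reproduce. All inputs in steps 3 to 6 except n=50 and the entry cut are assumptions.

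**3. Chance of a significant improvement with an inert device.** With two time points (BPQ, HADS), repeated measures ANOVA is equivalent to a paired t test. If the true device effect is zero and the non-specific improvement is d SDs of change, the probability of a significant improvement is P(T > t(0.975, n−1)), where T is noncentral t with n−1 degrees of freedom and noncentrality d√n. Two-sided 0.05 is assumed.

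| d | n = 50 | 40 completers |
|---|---|---|
| 0.2 | 28% | 23% |
| 0.3 | 55% | 46% |
| 0.4 | 79% | 69% |
| 0.5 | 93% | 87% |

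**4. How much drift the entry cut alone could cause.** For a normal score cut at c SDs from the population mean, the expected fall is (1−r) × φ(c)/(1−Φ(c)), where r is the screening-to-follow-up correlation. At c = 0 the second factor is 0.798, giving 0.40, 0.24 and 0.08 SD for r = 0.5, 0.7 and 0.9. With c between −0.5 and 0.5 the range is 0.05 to 0.57 SD. These are SDs of the screening score, not of change. The shift in TNSS is smaller if TNSS correlates imperfectly with the screening VAS.

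**5. Consequence for Aim 4.** Take an observed change of 0.5 SD as the between-group effect. Then n per arm = 2(1.960 + 0.842)²/0.5² = 62.8, so 63 for 80% power. Power at 63 per arm is Φ(δ√(63/2) − 1.960) for the true effect δ:

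| Non-specific part | True δ | Power at 63 per arm | n per arm for 80% |
|---|---|---|---|
| 0 | 0.5 | 80% | 63 |
| 0.1 | 0.4 | 61% | 99 |
| 0.2 | 0.3 | 39% | 175 |
| 0.3 | 0.2 | 20% | 393 |

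Dropout matters as well: to finish with 63 per arm, 63/0.80 = 79 must be enrolled at 80% retention, and 63/0.70 = 90 at 70%.

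**6. What 50 participants can say about retention.** Wilson 95% intervals: 35/50 (70%) gives 56% to 81%, half-width (0.809 − 0.562)/2 = 12 points; 40/50 (80%) gives 67% to 89%, half-width (0.888 − 0.670)/2 = 11 points. As a test of sharp cut-offs, take illustrative bands of at least 80% proceed, 60% to 79% amend, below 60% do not proceed. The interval for 35/50 touches all three bands. By the exact binomial, a true rate of 80% falls in the proceed band 58% of the time and the amend band 42%; a true rate of 60% falls below the lower cut-off 44% of the time.

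**The case against.** The strongest reply is that the plan asks whether a trial is warranted, not whether it is feasible, and states its purpose as estimating effect sizes. On that reading, looking for a signal is a legitimate pilot aim. This stands in part: only the feasibility/pilot label implies that feasibility will be shown. But even as a search for a signal, uncontrolled change cannot separate a device effect from drift, and no rule says what signal is enough.

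A reader might infer that the decision turns on whether the pre-post changes are significant. The documents do not support that. The Aim 2 hypotheses speak of significant improvement, but nothing makes significance the criterion for proceeding, Aims 1 and 4 are not tests of efficacy, and Aims 2 and 3 are marked preliminary.

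A reader might also infer that recruitment, dropout and adherence data will be missing. They will not: the records are collected. What is absent is a commitment to analyse and report them.

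Finally, feasibility results should not become the only basis for the decision. That would let a trial go ahead on good survey completion with no symptom signal. This objection stands, and the fix allows for it.

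**Conclusion.** The concern holds as a gap in the stated decision basis. Aims 1 to 4 are named as the means of deciding on a randomized trial; none covers a feasibility outcome, and no progression criterion is given. The device-effect evidence can look favourable without any device effect and cannot support the decision alone. Under assumed drift of 0.3 to 0.5 SD of change, a two-time-point comparison is significant 55% to 93% of the time at n=50. If 0.2 SD of an observed 0.5 SD is drift, a trial sized on 0.5 has 39% power instead of 80%. These figures show scale only: the documents give no SDs, correlations or retention rates, and step 5 treats SD of change as the planning SD.

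The sample of 50 can describe retention to within about 11 to 12 percentage points at 70% to 80%. That informs a decision but does not support sharp cut-offs.

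**What to change.** - **Add a feasibility aim**, using RedCap records already planned: consented per eligible screen and per month, week-5 retention, weekly survey completion and weekly device use, each with a 95% CI.
- **Set progression guidance before enrolment** that weighs these measures alongside the symptom estimates. State the half-width of about 11 to 12 points at 70% to 80% retention, so that thresholds are read as guidance.
- **Report Aim 2 changes as descriptive estimates with CIs**, and say that they include any non-specific improvement.
- **In Aim 4, do not size the randomized trial from the single-group effect sizes alone.** Show the sample size over a range of smaller between-group effects, and use the observed week-5 retention as the dropout input.
- **State the limits.** Retention among purchasers may not carry over to a randomized trial, and it says nothing about willingness to be randomized.

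The cost is protocol wording, one extra descriptive table and the need to commit to thresholds in advance. No new data collection is required.
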